
C. Approach

Design and Overview. This pilot study will examine the feasibility, acceptability, and preliminary impact of providing an In vivo intervention with NRT to increase NRT adherence compared to the control group. The intervention will be tested and refined initially with 10 participants in the In vivo NRT group (In vivo). Following the pre-pilot testing, 80 participants will be randomized to either the 1) In vivo or 2) Standard of Care (SC). All participants will complete approximately 60 minutes of baseline assessment to determine smoking history and characteristics prior to randomization, including previous experience with NRT. In vivo participants will be provided with each of the four forms of acute NRT (gum, lozenge, nasal spray, inhaler per week; counterbalanced across sessions by participant) to use in each 30 minute session in conjunction with a nicotine patch. In session, they will discuss their In vivo experience of using each combination NRT at each of the four sessions. To bolster their in vivo NRT experience, participants will be provided with a weekly sample of each NRT product to use between sessions to acclimate to the medication and to make PQAs. After the 4 week In vivo intervention period, participants will select their preferred acute NRT product to use with the nicotine patch (combination NRT; cNRT) to use for cessation over the next eight weeks. SC participants will receive four sessions of standard behavioral smoking cessation counseling and will select their preferred acute NRT (gum, lozenge, nasal spray, inhaler) based on product description. Thus, both groups will receive cNRT for 8 weeks total to make a quit attempt. All participants will continue to receive medication and monitoring for side effects, regardless of their medication adherence. Study visits occur at baseline (Week 0), intervention Weeks 1-4, medication selection/quit goal setting visit at Week 5, medication check (Week 6) Weeks 9 and 13 (end-of-treatment), and follow-up at one month later (Week 17; see Figure 1 for Study Design).

[figure not shown]
Preliminary Studies. The PI and her team have completed studies directly relevant to the current proposal and have worked with several different low income and disadvantaged populations such as individuals in the criminal justice system and Persons Living with HIV (PLWH).

Figure 1: Proposed Study Design from Recruitment to One Month Follow-up

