NRT Adherence	X	X	X	X	X	X	X	X	X	

Note: BL=Baseline Assessment; S=session; WK=week; M=month; PS=Product Selection; ¹All participants will complete these surveys twice (at the beginning and end of session) during sessions 1-4.

Randomization. We anticipate enrolling 10 pre-pilot participants in 3 months and 80 participants in 20 months and, based on our previous study with this population, expect to retain at least 70% through the one month follow-up point. Randomization will occur after completion of the initial screening and assessment.

Primary Outcomes. Feasibility and acceptability will be measured through high study retention (70%) and recruitment (recruitment of all participants within 24 months) in our groups. Additional items of acceptability include high scores on treatment satisfaction and credibility/expectancies that are equal or higher to the SC

group. Medication adherence is a third primary outcome with expected differences between our groups. Adherence is notoriously difficult to determine. Self-reported adherence is not always reliable, particularly during treatment studies where there is a demand characteristic to report the desired targeted behavior⁷³⁻⁷⁴ (e.g., adherence to NRT). The behavioral methods described under the assessment section represent the best available self-report tools for determining NRT adherence (e.g., TLFB report, returning used NRT patches and used product blister packs/packaging). Adherence will be defined by self-report using the TLFB and verified through returned patches and packaging. Good adherence is defined by taking greater than 80% of doses of medication at each time point. We have used these techniques in previous studies with low income populations with good compliance for use of TLFB verified by return of NRT materials⁷⁵.

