Participant Tracking and Retention. Participants will attend four weekly intervention sessions and a Product Selection session at Week 5. They will receive a one week follow-up after starting medication as well as monthly follow-up at weeks 9 and 13 during the NRT administration. The final follow-up will occur one month post-intervention. For this study, we will follow our participants for one month after the end of NRT administration (~4 months total in the study). We will continue to use our standard methods for ensuring high retention including collecting contact information on the participant as well as obtaining the contact information of three close friends or family members and providing follow-up and reminder phone calls. We have used these methods with good success with our ongoing and previous projects with this population. Thus, we believe we can maintain high retention and follow-up throughout the study.

Data Management and Statistical Analysis. Data will be entered and stored on the UAB secured network. Data analyses will be performed by the PI who has a master's degree in biostatistics using SPSS.

To test Aim 1, the development and refinement of the In vivo intervention, we will pre-pilot the intervention with 10 participants. We will examine participant's responses on the Treatment Satisfaction Survey as well as examine other factors that participants mention to improve treatment. As the intervention is already developed, this phase will be primarily used to finalize study procedures and make modifications to the study protocol. We will not conduct any in depth interviews or use qualitative methods, but will rather use this as an opportunity to make minor adjustments to the protocol.

To Test Aim 2, feasibility and acceptability of the intervention, we will determine our rate of recruitment, retention and the credibility and expectancies for the intervention using descriptive statistics. We expect that the novel In vivo intervention will be both feasible and acceptable as evidenced by a high rate of recruitment and over 70% retention through follow-up, with no differences in attrition between the groups. In addition, we expect that In vivo intervention will be rated as high on treatment satisfaction, credibility, and expectancies for treatment relative to SC. We will use Chi-Square analyses to examine attrition and t-tests to examine treatment satisfaction scores, credibility, and expectancy differences between the groups.

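### Aim 2 sets between-group equality criteria for acceptability and attrition but names only difference tests, whose non-significance cannot support equality

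*SAP*

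**What the plan says.** The SAP's Primary Outcomes paragraph names feasibility and acceptability first, and Study Design Considerations repeats that they are primary. Feasibility has two fixed benchmarks: 70% retention and full recruitment within 24 months. Acceptability adds a comparative element, namely high scores on "treatment satisfaction and credibility/expectancies that are equal or higher to the SC" group.

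Aim 2, under Data Management and Statistical Analysis, restates this. It expects a high recruitment rate and over 70% retention through follow-up, "with no differences in attrition between the groups", and expects the In vivo intervention to be "rated as high on treatment satisfaction, credibility, and expectancies for treatment relative to SC".

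Two kinds of analysis are given. The first is descriptive: recruitment rate, "retention and the credibility and expectancies for the intervention using descriptive statistics". The second is between-group: "We will use Chi-Square analyses to examine attrition and t-tests to examine treatment satisfaction scores, credibility, and expectancy differences between the groups". For Aim 2 the SAP states no equivalence or non-inferiority margin, no confidence-interval rule, no alpha and no power. Its warning about low power, under Aim 3, covers quit attempts and abstinence only.

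**The concern.** Chi-square and t-tests take no difference as the null hypothesis. A significant t-test in favour of In vivo would support the claim that its scores are higher. Nothing in either test can support the claim that scores are equal or that attrition does not differ. Failing to reject is weak evidence of similarity at any sample size, and it becomes more likely as the data become fewer or noisier.

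What is at stake is the conclusion on a primary outcome. The SAP intends this pilot to inform a full-scale trial if the intervention looks promising. If non-significance were reported as comparable acceptability or balanced dropout, that decision could rest on data equally compatible with clearly worse satisfaction or much higher dropout in the In vivo arm.

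**Working it through.** The SAP gives no calculation for Aim 2, so there is no figure to reproduce. The check asks what a non-significant result would leave open.

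**Inputs from the SAP**
- 80 randomized to two groups: "80 participants will be randomized to either the 1) In vivo or 2) Standard of Care (SC") (Design and Overview).
- Expected retention 70–80%, hence attrition 20–30% (Missing data).
- Satisfaction and credibility scales first given at Week 5 (Table 2).

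**Assumptions, because the documents are silent**
- 1:1 allocation, 40 per arm.
- Two-sided alpha 0.05, chi-square without continuity correction.
- Scores in SD units.
- Evaluable scores between 40 per arm (no loss) and 28 per arm (0.70 × 40).

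**Step 1. Attrition: width of the 95% interval when the observed rates are equal**

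Half-width = 1.96 × √[2p(1 − p)/40].
- p = 0.20: 1.96 × √(0.32/40) = 0.175, or 17.5 points.
- p = 0.30: 1.96 × √(0.42/40) = 0.201, or 20 points.

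**Step 2. Attrition: how often the chi-square is non-significant**

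All pairs of binomial counts (0–40 in each arm) were enumerated. The probabilities of pairs with |z| < 1.96 were summed, where z = (difference in proportions)/√[p̄(1 − p̄) × 2/40]. The sum was then restricted to pairs that also meet the 70% benchmark, read in two ways.

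| True attrition, SC vs In vivo | Non-significant | Non-significant and pooled retention > 70% | Non-significant and In vivo retention ≥ 70% |
|---|---|---|---|
| 20% vs 30% | 82% | 67% | 55% |
| 20% vs 40% | 50% | 24% | 12% |
| 30% vs 50% | 54% | 1% | 1% |

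The power of the chi-square alone is therefore about 18% for 20% vs 30% and 50% for 20% vs 40%.

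**Step 3. One concrete data set**

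Suppose 7/40 drop out under SC and 14/40 under In vivo.
- Pooled retention: 59/80 = 73.75%, above 70%.
- p̄ = 21/80 = 0.2625; z = 0.175/√(0.2625 × 0.7375 × 2/40) = 1.78; p = 0.075.
- 95% CI: 0.175 ± 1.96 × √(0.175 × 0.825/40 + 0.35 × 0.65/40) = 0.175 ± 0.189, or about −1 to +36 points.

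Observed dropout has doubled, the pooled benchmark is met and the test is non-significant. In vivo retention on its own is 26/40 = 65%, which only a per-arm report would show.

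**Step 4. Scores**

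Half-width in SD units = t(0.975, 2n − 2) × √(2/n).
- n = 40: 1.991 × √0.05 = 0.445.
- n = 28: 2.005 × √0.0714 = 0.536.

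Noncentral-t power for a true 0.3 SD deficit is 26% at 40 per arm and 20% at 28 per arm, so it is missed 74–80% of the time.

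**Sensitivity to allocation.** The Protocol's purpose section describes four intervention groups and one control group. If the five were equally weighted (64 vs 16), the half-widths would be 22–25 points for attrition and 0.56 SD for scores, so the problem would be larger.

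**The case against.** The strongest reply is that the SAP never says a p-value above 0.05 will be taken as equality. It states expectations, says the tests will examine differences, and plans descriptive statistics alongside. The score criterion can be read as a comparison of observed means, which a lower In vivo mean would fail. This stands: a reader might infer a rule that accepts the null, but the documents do not contain one. What they lack is any stated way to get from the named tests to the equality criteria.

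A reader might also infer that a doubling of dropout would pass as feasible half the time. That does not follow, because the 70% retention benchmark also applies. At 20% vs 40%, the chance of passing both falls to about 24% on pooled retention, or 12% if the In vivo arm must itself retain at least 70%. At 30% vs 50% the benchmark catches nearly everything. At 20% vs 30% both are passed 67% of the time on the pooled reading, but there the true In vivo retention is 70%.

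The SAP also plans sensitivity analyses of whether treatment differences depend on study completion. Outcome bias from dropout is therefore not left to the chi-square alone.

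Finally, formal non-inferiority may be too much for a pilot. With a 0.5 SD margin and truly identical arms, the lower 95% limit would exclude the margin only about 60% of the time at 40 per arm and 45% at 28 per arm; 80% power needs about 63 per arm. This stands as an objection to requiring a margin. It is not an objection to reporting intervals.

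**Conclusion.** The point holds as a gap between criterion and method. Part of the evidence for a primary outcome is equality with SC, and the only between-group methods named cannot supply it. At an assumed 40 per arm and two-sided 0.05, non-significance leaves open differences of roughly 18–20 points in attrition and 0.45–0.54 SD in scores. These sizes rest on the assumed allocation and alpha, and for scores on 28 to 40 evaluable per arm. The logical point does not depend on any of them.

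The documents do not support saying that the trial will declare equality from a non-significant test, or that the fixed benchmarks give no protection. The matter deserves correction because it changes what the trial may conclude and costs almost nothing. It does not call the sample size or the design of the pilot into question.

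**What to change.** In the SAP, Aim 2 paragraph:

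- Report In vivo minus SC differences in attrition, satisfaction, credibility and expectancy, each with a 95% confidence interval.
- Report retention in each arm against the 70% benchmark, as well as overall.
- Base the comparative acceptability statement on the estimate and its interval. State that a non-significant test will not be described as equality or absence of difference.
- Where the interval includes a materially worse In vivo result, call the comparison inconclusive.

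A margin stated in advance would make the last step sharper. It is optional and the sponsor's choice, given how often a margin of 0.5 SD would be inconclusive at this size.

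The cost is SAP wording; no new data or participants are needed. The downside is that the comparative claim will be weaker, or inconclusive, more often with 80 participants.

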## Measurement Occurrence Chart

Data Collection Instrument	Baseline (1)	Wk1 (2)	Wk2 (3)	Wk3 (4)	Wk4 (5)	Wk5 (6)	Wk6 (7)	Wk9 (8)	Wk13 (9)	M1FU (10)
Screening Questionnaire (survey)										
Session Status (survey)										
Med Given (survey)		✓	✓	✓	✓	✓	✓	✓	✓	✓
CO Level	✓	✓	✓	✓	✓	✓	✓	✓	✓	✓
Cotinine Test	✓	✓	✓	✓	✓	✓	✓	✓	✓	✓
Pregnancy Test	✓				✓		✓	✓	✓	
Urine Drug Screen	✓									
Mini International Neuropsychiatric Interview Mini	✓									
Demographic Form (survey)	↓									
NRT Adherence (survey)		↓	↓	↓	↓	↓	↓	↓	↓	↓
Minnesota Nicotine Withdrawal Scale Pre (survey)	↓	↓	↓	↓	↓	↓	↓	↓	↓	↓
Questionnaire Of Smoking Urges Short Form Pre (survey)	↓	↓	↓	↓	↓	↓	↓	↓	↓	↓
Smoking History Form (survey)	↓									
Weekly Smoking Behavior	✓	✓	✓	✓	✓	✓	✓	✓	✓	✓
Thoughts About Abstinence (survey)	↓	↓	↓	↓	↓	↓	↓	↓	↓	↓
Fagerstrom Test For Nicotine Addiction (survey)	↓					↓	↓	↓	↓	↓
Perceived Stress Scale (survey)	↓	↓	↓	↓	↓	↓	↓	↓	↓	↓
Wisconsin Inventory of Smoking Dependence Motives (survey)	↓					↓	↓	↓	↓	↓
Treatment Expectations (survey)	↓	↓	↓	↓	↓	↓	↓	↓	↓	↓
Smoking Abstinence Questionnaire (survey)	↓					↓	↓	↓	↓	↓
Abstinence Related Motivational Engagement ARME (survey)	↓	↓	↓	↓	↓	↓	↓	↓	↓	↓
Attitudes About Nicotine Replacement Therapy (survey)	↓	↓	↓	↓	↓	↓	↓	↓	↓	↓
Treatment Satisfaction Survey (survey)						↓		↓	↓	↓
Credibility Expectancy Questionnaire CEQ (survey)						↓		↓	↓	↓
Symptom Side Effects (survey)	↓	↓	↓	↓	↓	↓	↓	↓	↓	
Barratt Impulsivity Scale	✓									
Pittsburgh Sleep Quality Index	✓	✓	✓	✓	✓	✓	✓	✓	✓	✓
Minnesota Nicotine Withdrawal Scale Post (survey)	↓	↓	↓	↓	↓	↓				
Questionnaire Of Smoking Urges Short Form Post (survey)	↓	↓	↓	↓	↓	↓				
Alliance Questionnaire						✓				
Alliance Questionnaire Therapist						✓				
Group Assignment (survey)										
Audio Recording Length		✓	✓	✓	✓	✓				

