
These studies demonstrate our experience developing interventions with low income populations and the significance of the proposed approach. However, while our data as well as previous NRT sampling interventions are suggestive of the importance of NRT experience for subsequent cessation, pilot data are needed to determine the mechanisms of action associated with medication adherence. We will examine whether providing an In vivo NRT sampling intervention increases adherence over SC and whether this is due to increased positive NRT expectancies and abstinence self-efficacy as well as decreases in withdrawal and cravings. This is a necessary first step prior to launching a larger clinical trial examining this In vivo intervention for increasing abstinence.

Participant Availability, Feasibility and Rate of Enrollment. Participants will be recruited from the Birmingham metro community with flyers hanging at different community locations that serve low income smokers (e.g., bus stops, medical student run medical clinic servicing indigent patients, etc.). Based on our previous studies with similar populations as well as the high rates of smoking in Alabama, we do not anticipate any problems in recruiting the necessary study population. In our previous study with community corrections smokers, we screened 650 potential participants in 40 months to randomize 500, with most participants excluded due to medical contraindications for bupropion. Recruiting 10 participants in 3 months and 80 participants over 20 months would require enrollment of approximately 3-4 participants per month. Given that our team recruited a similar low income population of 500 participants within 40 months of recruitment (8 months earlier than projected), enrollment is very feasible. Further, while we will not focus specifically on participants with criminal justice involvement, individuals in the criminal justice system but serving their time in the community will not be excluded if they meet the other enrollment criteria.

Inclusion Criteria. a) 18 years or older; b) qualifying as low income (as defined by making <150% above the poverty line or <\$22,260 as a single or <\$45,570 for a family of four); c) Smoking at least 5 cpd for the past year and a CO>10ppm to ensure daily smoking. This relatively low cutoff was chosen due to the expectation of

enrolling a large $\geq 50\%$ African-American average <10 CPD compared to Whites who average ~ 15 CPD.; and d) English speaking.

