Screening Questionnaire. Participants will be asked basic screening questions prior to consent for the study to determine initial eligibility including: age, income, currently pregnant or nursing, average CPD, latex allergy, myocardial infarction in past month, and years of smoking. (3 min)
Demographics. Basic demographic information will be collected including age, gender, race/ethnicity, education level, employment status, marital and living situation, monthly income, and history of substance use and mental illness. (1 min)
Urine Drug Screen. All participants will be screened for drug use during baseline assessment. We will test for alcohol (using ethyl glucuronide) as well as amphetamines, barbiturates, benzodiazepines, cannabis, cocaine, opiates, and methadone. (1 min)
Smoking History. Questions about smoking history will include age of smoking initiation, age of regular use, us of other tobacco products, number of years of smoking, average cigarettes smoked per day, previous quit attempts, time since last quit attempt, difficulty of last quit attempt, previous smoking cessation treatment (e.g., use of NRT, bupropion, varenicline), family members who smoke, and family and personal medical problems related to smoking. (10 min)
Treatment Expectancies. This assessment queries expectancies about the efficacy of various forms of smoking pharmacotherapy (e.g., nicotine gum, patch, lozenge, inhaler, nasal spray, varenicline, and bupropion) as well as behavioral interventions (e.g., group, individual, self-help materials, hypnosis) using the question, "How much do you think _____ will help you to quit smoking". These questions are answered using 1-7 Likert scale. This is a scale we developed and used in our studies with this population. (5 min)
Perceived Stress Scale – 10 Item (PSS-10⁵⁹). This is a self-report questionnaire that assesses a person's stress in the past month. It utilizes a 5-point Likert scale ranging from "Never" to "Very Often". (1 min)
Thoughts About Abstinence Questionnaire – 4 Items (TAA)⁶⁰. This survey assesses 1) motivation to quit; 2) expected difficulty quitting; 3) confidence in one's ability to quit (abstinence self-efficacy); and 4) abstinence goals. (1 min)

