To test Aim 3, we will examine medication adherence during the 8 week intervention period between the intervention groups using Chi Square analyses at weeks 6, 9 and 13. Medication adherence will be defined as a self-reported use of taking 80% of medication as prescribed at each time point for both groups (adherent or not adherent). We can also look at adherence as a continuous proportion variable: adherence = number of doses taken / the number of doses given. We will also examine demographic and smoking characteristics (particularly withdrawal, cravings, abstinence self-efficacy, and NRT perceptions) that would be associated with medication adherence at weeks 6, 9 and 13 using logistic regression. These analyses will allow us to examine important associations with medication adherence in these groups.

To examine underlying factors believed to be important for medication adherence, particularly withdrawal, craving, self-efficacy, and perceptions of NRT, we will also examine these factors by intervention groups across time using paired t-tests, as appropriate. We are primarily interested in determining if our In vivo group had decreases in withdrawal and cravings, while increasing abstinence self-efficacy and NRT perceptions relative to the SC group. Given the pilot nature of this intervention, we will be able to examine 24-hour quit attempts and abstinence, but these factors are not the main focus on analyses as we will likely be underpowered to find significant differences on these outcomes with this small of a sample. While 80 participants may seem like a fairly large sample for a pilot study, a sample size between 500-600 participants is typical for most smoking cessation interventions and would be needed to examine important moderators and mediators of cessation. However, we will be able to obtain initial effect sizes that will be useful for determining the appropriate sample size for a fully-scaled R01 project in the future, if this intervention appears promising.

Missing data. There is a high likelihood that we will have participants who may miss an appointment, do not complete the study, or are otherwise lost to follow-up. Because of the potential of bias due to non-missing

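### For withdrawal, craving, self-efficacy and NRT perceptions the SAP asks about change relative to standard care (SC), but the only test it names is a within-arm paired t-test

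*SAP*

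**What the plan says.** The SAP section Data Management and Statistical Analysis, under Aim 3, singles out four factors thought to drive adherence: withdrawal, craving, self-efficacy and perceptions of NRT. On method it says "we will also examine these factors by intervention groups across time using paired t-tests, as appropriate". The next sentence gives the main interest: whether the In vivo group had less withdrawal and craving "while increasing abstinence self-efficacy and NRT perceptions relative to the SC group".

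Two neighbouring analyses come close. Under Aim 3, a search for characteristics "that would be associated with medication adherence at weeks 6, 9 and 13 using logistic regression" includes these same factors. Under Aim 2, the SAP plans "t-tests to examine treatment satisfaction scores, credibility, and expectancy differences between the groups".

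The reason for measuring the factors is in the summary that closes Preliminary Studies. It says "pilot data are needed to determine the mechanisms of action associated with medication adherence" and asks, should In vivo raise adherence over SC, "whether this is due to increased positive NRT expectancies and abstinence self-efficacy as well as decreases in withdrawal and cravings". The protocol is a manual of procedures and has no analysis section.

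**The concern.** A paired t-test compares two time points in the same people. Run by group, it asks of each arm whether that arm moved from its own earlier value. The stated question is whether one arm moved more than the other, and two within-arm p-values do not answer that.

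What is at stake is the mechanism argument. Saying that an adherence gain is due to these factors needs two links: arm to factor, and factor to adherence. The second has a named method, the logistic regression. The first does not. The visit for the comparison is also unnamed, so it could be chosen after the results are seen.

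**Working it through.** **1. Does any other analysis supply the contrast?**

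- Aim 2 t-tests are between groups, but for satisfaction, credibility and treatment expectancy. Expectancy there is listed with credibility, which Table 1 measures with the Credibility and Expectancy Questionnaire.
- The Aim 3 logistic regression has adherence as outcome and the factors as predictors. It gives no arm difference in a factor.
- The Aim 3 remark on obtaining effect sizes for a later trial names neither outcome nor contrast.
- The chi-square tests cover attrition and adherence.

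So no between-arm method is named for these four factors.

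**2. Which visits could carry a between-arm comparison?** I read NRT perceptions as the attitudes scale (ANRT-12) and self-efficacy as the confidence item of Thoughts About Abstinence. The manual's Measurement Occurrence Chart schedules both, and the withdrawal and craving scales, at Baseline and at Weeks 5, 6, 9 and 13.

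- *Week 5.* SC has been dispensed no NRT in Weeks 1-4 (Medication Dispensing, Control Group). SC participants complete their questionnaires at step 4 and receive NRT at steps 15-16 (Therapy Protocol, Control Group, Week 5). Scores therefore fall after the four sessions and before SC starts NRT. In vivo participants, however, answer after an instruction not to smoke overnight (Group A, Week 4, step 25) and with a patch already placed (Group A, Week 5, step 5). That directly disturbs withdrawal and craving. It may also affect self-efficacy and attitudes, less directly.
- *Week 6.* Neither arm's Week 5 steps carry forward an instruction to refrain, so this is the first visit with matching instructions. Both arms have by then had a week of combination NRT, so scores may partly reflect adherence.

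**3. Illustration of reading two paired tests side by side.** The documents give no alpha, SD or effect size for these factors, so there is no stated figure to reproduce.

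Inputs from the SAP: 80 randomized (Design and Overview); at least 70% retained to the one-month follow-up (Randomization), so 0.70 × 80 = 56.

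Assumed: 1:1 allocation (no ratio is stated), giving 40 or 28 per arm; two-sided alpha 0.05; the same true change d in both arms, in SDs of the change score.

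Power p of each paired test is P(T > t(0.975, n-1)), with T noncentral t on n-1 df and noncentrality d√n. The chance that In vivo is significant and SC is not is p(1-p).

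| d | p, n=40 | p(1-p) | p, n=28 | p(1-p) |
|---|---|---|---|---|
| 0.2 | 0.234 | 0.179 | 0.174 | 0.144 |
| 0.3 | 0.456 | 0.248 | 0.334 | 0.222 |
| 0.4 | 0.694 | 0.212 | 0.532 | 0.249 |
| 0.5 | 0.869 | 0.114 | 0.723 | 0.200 |
| 0.8 | 0.9985 | 0.0015 | 0.983 | 0.017 |

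A two-sample t-test on the change scores favours In vivo in 2.5% of such trials, by construction and in simulation.

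Allocation matters. The manual describes four In vivo groups and one control. If all five were equal in size (64:16, an assumption), the chance is p₆₄(1-p₁₆): 0.350 × 0.887 = 0.31 at d = 0.2, 0.883 × 0.678 = 0.60 at d = 0.4, and 0.976 × 0.535 = 0.52 at d = 0.5.

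**4. Precision of the direct estimate.** For a baseline-adjusted difference at one visit, the 95% CI half-width in SDs of the score is t(0.975, 2n-3) × √((1-r²) × 2/n), where r is the baseline correlation (assumed). At n = 40 and r = 0.5: 1.991 × √(0.75 × 0.05) = 0.39.

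| r | n=40 | n=28 |
|---|---|---|
| 0.3 | 0.42 | 0.51 |
| 0.5 | 0.39 | 0.46 |
| 0.7 | 0.32 | 0.38 |

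That is wide, but it is the effect size and uncertainty a pilot is meant to deliver.

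**The case against.** **The comparison is intended.** The SAP examines the factors by intervention group, states the comparison with SC, and qualifies the test with a phrase allowing alternatives. A difference could be worked out later from each arm's mean change and SD. This stands. A reader might infer that no comparison with SC is planned at all, and the text does not support that. What is missing is a named method and visit.

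**The comparator may govern only half the sentence.** It follows self-efficacy and perceptions directly and may not reach withdrawal and craving. For the pre- and post-session scales, a paired t-test is a natural within-arm test. This also stands as a matter of wording. But the Preliminary Studies summary treats all four as reasons for an adherence gain over SC, so the between-arm question arguably covers them all.

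**The percentages are not from the plan.** They need a decision rule the SAP never states, plus assumed effects and allocation. They shrink to 0.15% and 1.7% at 0.8 SD. The 28 per arm applies retention at Week 17 to Weeks 5-6, so it is a pessimistic bound there. All correct: the figures show why side-by-side paired tests are a poor substitute, and they do not forecast this trial's error rate.

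**The factors are secondary in an 80-person pilot.** True, and it limits the weight of the point. It does not make the named test answer the question.

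**Conclusion.** The point holds for the named method. The SAP puts a between-arm question, explicitly for self-efficacy and NRT perceptions and arguably for all four factors, and names only a within-arm test.

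Its reach is limited to the arm-to-factor half of the mechanism argument. A reader might infer that the adherence result is compromised. It is not: adherence has its own between-group chi-square at Weeks 6, 9 and 13, and attrition, satisfaction, credibility and expectancy also have between-group tests.

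The size, 11-25% at 40 per arm and 14-25% at 28 per arm against 2.5%, rests on the assumed p<0.05 rule, 1:1 allocation and equal true changes of 0.2-0.5 SD.

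**What to change.** For each factor, replace the paired t-test as the inferential analysis with an adjusted In vivo minus SC difference and 95% CI. Use ANCOVA on the score at one pre-named visit with the baseline score as covariate. A mixed model limited to the named visits would also serve. One with unstructured covariance over all nine post-baseline visits would need 9 × 10 / 2 = 45 covariance parameters, which is heavy for 80 participants. Label the results secondary and exploratory.

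- **Self-efficacy and NRT attitudes:** Week 5. State that In vivo participants answer after an overnight-abstinence instruction and with a patch on.
- **Between-visit withdrawal and craving:** Week 6. State that scores from then on may partly reflect adherence.
- **In-session withdrawal and craving:** also report the between-arm difference in post-session score adjusted for pre-session score, with 95% CI. Interpret it as the effect of the whole package, because only In vivo participants are told to refrain from smoking and use NRT in session.
- **Paired t-tests:** keep as within-arm description.

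Two reconciliations are needed:

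- The manual's Baseline Appointments, Procedures, step 11 places the Baseline questionnaires after randomization. The SAP's Design and Overview and Randomization sections place assessment before it. Settle this so that the baseline covariate precedes allocation.
- The pre/post scales are set for Sessions 1-4 in SAP Tables 1 and 2, and for Weeks 1-5 in the manual's Data Collection Parameters. The Measurement Occurrence Chart also marks the post scales at Baseline.

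The cost is SAP wording and those two reconciliations. SPSS, already the planned software, fits these models. All four measures are already scheduled at Baseline and the visits named, so no new data are needed.
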